12.1.4.4. Day 71 (+5 Days) End of Treatment/Early Termination

The following procedures will be performed on Day 71:

1. Record concomitant medications/procedures (section [12.2](#))
2. Measurement of body weight
3. Vital sign measurements (section [14.8](#))
4. Collection of samples for:
 - a. Clinical laboratory testing (section [14.7](#))
 - b. Anti-AUX-I and anti-AUX-II antibody testing (section [14.7.1](#))
5. Digital photograph of selected quadrant (section [13.1](#))
6. Subject cellulite assessments of the selected quadrant using the photographic image
(NOTE: complete subject cellulite assessments before Investigator cellulite assessments) using:
 - a. PR-PCSS assessment (section [13.1.1.1](#))
 - b. S-GAIS (section [13.1.1.2](#))
 - c. Subject satisfaction with cellulite treatment assessment (section [13.1.1.3](#))
7. Investigator cellulite assessments of selected quadrant independently conducted; ie, with no knowledge of the subject's rating, using:

- a. CR-PCSS live assessment of subject (section 13.1.1.4)
- b. Hexsel CSS assessment of live subject while subject is standing in a relaxed position (section 13.1.1.6)
- c. I-GAIS (section 13.1.1.5)
- 8. Injection site reactions and local tolerability
- 9. AEs (section 14)

12.1.4.5. Follow-up Visits

Following the Day 71 visit, the quadrant(s) treated with EN3835 in the open label study will be evaluated every 3 months from the first exposure to EN3835 following the schedule in [Table 2](#). The first follow-up visit will be approximately 20 days after the Day 71 visit (ie approximately Day 90 after treatment session 1). Follow-up visits will continue until the study is terminated when at least 100 subjects have been assessed at 12 months after the first exposure to EN3835.

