12.1.3.1. Three-Month Assessments

Subjects will return within 20 days (± 4 days) of completion of the double-blind study for the first of 4 safety and cellulite severity evaluation visits. Assessments to be completed at these visits are detailed in Table 2. Subjects are to return at 3-month intervals until they have completed 12 months from Day 1 of the double-blind study. At these visits, the quadrant previously treated with EN3835 in the EN3835-201 study or quadrants treated with EN3835 in the open-label study

will be evaluated. If the quadrant treated in study EN3835-201 is retreated in the open-label study, the 3-month assessments will reset to treatment visit 1/Day 1 of the open-label treatment and the study visits will continue as described in [Table 3](#) followed by 3-month assessments as described in [Table 2](#). If a different quadrant is treated in the open-label study, the 3-month assessments of both the quadrant treated in the double-blind study (EN3835-201) and the quadrant treated in the open-label study will continue.

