At each treatment course, subjects will receive 3 treatment sessions (Day 1, Day 22, and Day 43) unless the chosen quadrant has no further treatable edematous fibrosclerotic panniculopathy (EFP) dimples and the Investigator rates the quadrant a score of 0 on the Clinician Reported Photounumeric Cellulite Severity Scale (CR-PCSS). The same dimples within a quadrant or different dimples within a quadrant may be treated at each session but injections must all be within the selected quadrant for all 3 sessions. Each treatment session will be separated by approximately 21 days. Day 71 visit (end of treatment/early termination [EOT/ET]) will be performed for each subject. After Day 71, the subjects will be observed every 3 months from their first exposure to EN3835 up to a maximum of 1 year in each treated quadrant (including

both open-label and double-blind treated quadrants, if different quadrants were treated across both studies). Durability beyond Day 360 will be assessed in subjects who received active treatment in EN3835-201 and showed a composite improvement of at least 1 level on both the CR-PCSS and the Patient Reported Photonic Cellulite Severity Scale (PR-PCSS). In these subjects, the original quadrant treated in EN3835-201 will be assessed until the end of the current study, in addition to any treated quadrants occurring in the current study. Assessments of durability beyond Day 360 may also include subjects who opted not to receive additional treatments in EN3835-202.

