1.2. Schedule of Study Assessments

[Table 2](#) lists the schedule of observation assessments, [Table 3](#) lists the schedule of treatment session assessments, [Table 4](#) lists the schedule of long-term durability assessments.

The schedule of observation assessments is applicable for both observation only and treated subjects in current study. For example, if subjects received treatments (ie, re-treatment, re-dosing, or a first treatment) in current study may be scheduled for observation assessments up to maximum of 1 year for each treated quadrant.

NOTE: Observation visits ([Table 2](#)) in the open-label extension study begin after completion of double-blind study (Day 71). Treatment sessions ([Table 3](#)), if elected, will begin after study drug blind is broken in study EN3835-201 while observation visits continue concurrently. Durability visits ([Table 4](#)) are for the subjects who received active treatment in EN3835-201 and scored an improvement of at least 1 level on both the CR-PCSS and the PR-PCSS at the same visit on or before Day 71 in the double-blind study EN3835-201.

Table 2: Schedule of Observation Assessments

Procedures	Screening A ^a (≥Day 71 Visit of Double-blind Study)	Visit 1 Day 90 ^b (±7 days)	Visit 2 Day 180 ^b (±7 days)	Visit 3 Day 270 ^b (±7 days)	Visit 4 End of Study/ Early Termination Day 360 ^{b,f} (±7 days)
Informed Consent	X				
Inclusion/Exclusion	X				
Digital photography		X ^c	X ^c	X ^c	X ^c
Prior/Concomitant Medications/Procedures	X	X	X	X	X
Body weight		X	X	X	X
Vital signs		X	X	X	X
Collection of samples:					
• Clinical laboratory					X
• Anti-AUX-I/anti-AUX-II antibody level					X
Subject cellulite assessments:					
• Patient Reported Photonumeric Cellulite Severity Scale (PR-PCSS)		X ^{d,e}	X ^{d,e}	X ^{d,e}	X ^{d,e}
• Subject Global Aesthetic Improvement (S-GAIS)					X ^{d,e}
• Subject satisfaction with cellulite treatment assessment					X ^{d,e}
Investigator cellulite assessments:					
• Clinician Reported Photonumeric Cellulite Severity Scale (CR-PCSS)		X ^e	X ^e	X ^e	X ^e
• Hexsel Cellulite Severity Scale (CSS)					X ^e
• Investigator Global Aesthetic Improvement (I-GAIS)					X ^e
Injection site reactions/local tolerability in assigned quadrant from EN3835-201 study		X	X	X	X
Adverse events		Monitored Throughout Study			

^a Informed consent for open-label observation assessments and optional treatment election.

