^b Four (4) visits at 3-month periods begin 90 days after Day 1 of the double-blind study (EN3835-201) (ie, within 20 days \pm 4 days of completion of double-blind study).

^c Only the treated quadrant(s) is photographed. For subjects participating in observation-only visits, the quadrant treated in the double-blind study (EN3835-201) is photographed; for subjects with open-label treatment (treated with EN3835 in study EN3835-202), the treated quadrant is photographed.

^d Assessment made via viewing digital image photograph.

^e Assessment of treated quadrant(s) only.

^f For subjects treated with active EN3835 in the double-blind study and having a different quadrant treated in the open-label study, refer to [Table 4](#) for continued assessments of the double-blind treated quadrant for durability beyond Day 360. NOTE: Subject cellulite assessments must be completed before the Investigator cellulite assessments are conducted at each visit.

NOTE: Subject cellulite assessments must be completed before the Investigator cellulite assessments are conducted at each visit.

Table 3: Treatment Session Assessments

Procedures	Screening B ^a (Day -14 to -1 relative to Tx Visit 1)	Tx Visit 1 Tx Session 1 Day 1	Tx Visit 2 Tx Session 2 Day 22 (± 3 days)	Tx Visit 3 Tx Session 3 Day 43 (± 3 days)	Tx Visit 4 End of Treatment/ Early Termination Day 71 (+5 days) ^b	
Inclusion/Exclusion	X					
Digital photography	X ^c	X ^{c,d}	X ^{c,d}	X ^{c,d}	X ^c	
Medical history/EFP history including previous treatments	X ^{k,m}					
Prior/Concomitant Medications/Procedures	X ^{k,m}	X ^m	X	X	X	
Physical examination:	X					
• Body weight	X ^m		X ^e	X ^e	X	
• Height	X ^m					
Vital signs	X	X ^f	X ^f	X ^f	X	
12-lead ECG	X ^l					
Collection of samples:						
• Clinical laboratory	X ^m				X	
• Anti-AUX-I/anti-AUX-II antibody level		X ^{e,m}			X	
• Urine pregnancy testing	X	X ^e	X ^e	X ^e		
Subject cellulite assessments:						
• Patient Reported Photounumeric Cellulite Severity Scale (PR-PCSS)	X ^{g,h}		X ^{e,g,h}	X ^{e,g,h}	X ^{g,h}	
• Subject Global Aesthetic Improvement (S-GAIS)					X ^{g,h}	
• Subject satisfaction with cellulite treatment assessment					X ^{g,h}	
Investigator cellulite assessments:						
• Selection of dimples to be treated within selected quadrant		X ^e	X ^e	X ^e		
• Marking the dimples to be treated within selected quadrant		X ^e	X ^e	X ^e		
• Clinician Reported Photounumeric Cellulite Severity Scale (CR-PCSS)	X ^h		X ^{e,h}	X ^{e,h}	X ^h	

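### The starting point for follow-up of a quadrant given a second EN3835 course is stated inconsistently, so the visit labelled Day 360 can mean different times since re-exposure

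*Combined protocol and SAP*

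**What the plan says.** Four places set the starting point of the 3-month visits.

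- **Protocol 12.1.3.1 (Three-Month Assessments).** The default is 12 months from Day 1 of EN3835-201. If the quadrant treated there is treated again in EN3835-202, "the 3-month assessments will reset to treatment visit 1/Day 1 of the open-label treatment".
- **Protocol 12.1.4.5 (Follow-up Visits).** The first sentence says that "the quadrant(s) treated with EN3835 in the open label study will be evaluated every 3 months from the first exposure to EN3835". Read literally, for a woman given active drug in EN3835-201 that date is Day 1 of the parent study. The next sentence counts from the open-label course: "The first follow-up visit will be approximately 20 days after the Day 71 visit (ie approximately Day 90 after treatment session 1"). The section sets no 12-month limit per woman: "Follow-up visits will continue until the study is terminated when at least 100 subjects have been assessed at 12 months".
- **SAP 1.1 (Description of Study Design).** After Day 71 subjects are "observed every 3 months from their first exposure to EN3835 up to a maximum of 1 year in each treated quadrant". This is said to include "both open-label and double-blind treated quadrants, if different quadrants were treated across both studies". Nothing is said about one quadrant treated in both studies.
- **SAP 1.2, Table 2 footnote b.** The four "visits at 3-month periods begin 90 days after Day 1 of the double-blind study (EN3835-201"). No other origin is given, although Table 3 footnote b sends women to Table 2 after open-label treatment. The text of SAP 1.2 names re-treatment and says that treated subjects "may be scheduled for observation assessments up to maximum of 1 year for each treated quadrant", but not from which day the year runs.

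**The concern.** For a re-treated quadrant, first exposure to EN3835 comes before the course being followed. A clock started at first exposure has partly run down when re-treatment begins; a clock started at open-label Day 1 has not. Both cannot govern the same visits.

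Safety and immunogenicity of re-treatment is a secondary objective (protocol 9.2, SAP 1.3.2). In the SAP schedule, the only laboratory and antibody samples after open-label Day 71 are at Visit 4, labelled Day 360. SAP 7.7 reports antibodies at Days 1, 71 and 360, and SAP 6.2 summarises severity by study day. If the label is counted from different dates, one Day 360 column pools women at different times since re-exposure.

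A former-placebo woman can also receive two EN3835-202 courses in one quadrant. Protocol 12.1.4 places her second course in the re-treatment arm, but the reset in 12.1.3.1 is worded only for a quadrant treated in EN3835-201.

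**Working it through.** **1. The plan's own figure.** Day 71 plus about 20 days is 71 + 20 = 91, within the ±7-day window of Day 90, counted from open-label session 1. This fits only the open-label clock. Re-treatment cannot start before EN3835-201 Day 71, so open-label Day 71 falls on EN3835-201 Day 71 + 70 = 141 or later, already past Day 90 on the parent clock.

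**2. The literal first-exposure reading with the SAP's 1-year maximum.** Let X be the EN3835-201 day on which re-treatment starts. The documents give neither an unblinding day nor a re-treatment day, so X is an assumption and a range is shown.

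- Days of the year left = 360 − X; share lost = X/360.
- Open-label Day 71 falls on EN3835-201 Day X + 70.
- A visit on EN3835-201 Day d is open-label Day d − X + 1.

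| X | Days left | Share lost | Open-label Day 71 on EN3835-201 clock | Later visits: EN3835-201 day → open-label day |
|---|---|---|---|---|
| 90 | 270 | 25% | 160 | 180→91, 270→181, 360→271 |
| 120 | 240 | 33% | 190 | 270→151, 360→241 |
| 180 | 180 | 50% | 250 | 270→91, 360→181 |
| 210 | 150 | 58% | 280 | 360→151 |
| 270 | 90 | 75% | 340 | 360→91 |
| 290 | 70 | 81% | 360 | none |

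From about X = 290 no visit follows open-label Day 71. For X = 120 or 210 the remaining visits (Days 151, 241) fit no scheduled visit window on the open-label clock.

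**3. Second EN3835-202 course in the same quadrant.** Protocol 10.1 lets it begin as early as Day 71 of the first course. Counted from the first course, 360 − 71 = 289 days are then left, a loss of 71/360 = 20%. A later start loses more.

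**4. The reset reading.** Visits fall at X + 90, X + 180, X + 270 and X + 360, so the origin itself costs nothing. The end-of-study rule still applies. Planned enrolment is 0.95 × 350 = 332.5, stated as 333. With 1:1 randomisation about 332.5/2 ≈ 166 of these had active drug in EN3835-201. The study may end once 100 women reach 12 months after first treatment in either study (protocol 10.1, 12.5), which can happen before re-treated women reach X + 360.

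**The case against.** The strongest reply is that the protocol already settles the main case. Section 12.1.3.1 gives a default and then an express exception for re-treatment, and the Day 90 sentence of 12.1.4.5 works only on the open-label clock. Since 12.1.4.5 is about quadrants treated in the open-label study, first exposure there may simply mean the first session of that course. In the SAP, section 1.2 allows up to a year per treated quadrant and names re-treatment. The treatment phase in SAP 2 runs from the quadrant's first EN3835-202 treatment to study end. Adverse events are monitored throughout, and SAP 7.4 defines treatment-emergent events per course with no 1-year cut-off. The open-label durability population leaves out quadrants already given EN3835 in EN3835-201.

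Most of this stands. The protocol leans clearly towards the open-label clock for an EN3835-201 quadrant, and the adverse event and durability analyses are little affected for that group. It does not remove the inconsistency. SAP 1.2 gives no starting day, the treatment phase is an analysis period and not a visit schedule, footnote b still names only the parent study, and nothing covers the second same-quadrant EN3835-202 course.

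Version differences may explain part of the gap. The protocol text compared is Amendment 2, while the SAP includes durability visits to Day 720 that this text lacks, so the SAP may follow a later amendment. The Amendment 2 synopsis and schedule footnotes are not in the text available here and could not be checked.

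**Conclusion.** The inconsistency is real and should be removed. The potential loss in the table arises only if the SAP wording is applied literally, and its size depends on an assumed start day.

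A reader might infer more than the documents support:

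- **That re-treated women lose half or more of their follow-up.** This needs the literal SAP reading and a start on or after EN3835-201 Day 180. Late starts are foreseeable, since protocol 14.9 provides for a Screening B visit more than 12 months after the parent-study ECG, but no date is given.
- **That 12.1.4.5 itself cuts follow-up short.** It has no limit per woman; the 1-year maximum that creates the loss is in SAP 1.1.
- **That no laboratory or antibody sample is taken after re-exposure.** Open-label Day 71 samples are planned. For starts before about Day 290, the Visit 4 sample also falls after re-exposure and after Day 71. What varies is its timing.
- **That the reset clock secures four visits to Day 360.** The 100-subject rule can end follow-up earlier on either clock.

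**What to change.** Reconcile the passages to one origin, consistent with what 12.1.3.1 already states:

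- In protocol 12.1.4.5 and SAP 1.1, replace first exposure to EN3835 with Day 1 of the EN3835 course given in that quadrant (for a re-treated EN3835-201 quadrant, the open-label course).
- Add the same origin to SAP Table 2 footnote b for quadrants treated in EN3835-202.
- State whether it also applies to a second EN3835-202 course in the same quadrant.
- Define study day for SAP 6.2 and 7.7 from that date, so that each Day 360 column holds one time since exposure.

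The cost is wording in three places and one study-day definition. Some re-treated women would attend later visits, which 12.1.3.1 already requires. Because the end-of-study rule can still cut these visits, the report should show how many re-treated women reached each visit.

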12.2. Prior and Concomitant Medications and Procedures

All medications (including over-the-counter medications) taken by the subject at screening visit 1 through the end of the study must be recorded.

Additionally, any diagnostic, therapeutic or surgical procedures performed during the study period should be recorded including the date, indication for and description of the procedure.

12.2.1. Prohibited Medications

The following medications are prohibited for those subjects that elect to have treatment with study drug during the treatment phase of the study: anticoagulants (warfarin, heparin, direct thrombin inhibitors, Factor X inhibitors) and antiplatelet agents (aspirin >150 mg/day and P2Y12 inhibitors, such as clopidogrel), which can cause additional bruising. However the use of aspirin at a dose level of \leq 150 mg per day will be permitted during the treatment phase of the study. For those subjects in the observational-only phase of study, there are no prohibited medications.

Table 5: Concomitant Medication Restrictions for Subjects During the Treatment Phase of Study

Drug Class	Restrictions
Anticoagulants	Subjects who elect treatment cannot take antiplatelet agents or anticoagulants (except for \leq 150 mg aspirin daily) within 7 days before and after the dosing administration.

12.2.2. Prohibited Procedures

The treatments and procedures listed in exclusion criteria are prohibited during the study.

12.3. Treatment Compliance

All subjects who elect to have treatment will receive study drug administered by a clinician at the investigator's site.

Accidental or intentional overdoses should be reported to the Sponsor/designee promptly (see section [14.6.2](#)).

12.4. Blinding and Randomization

This study will be conducted as an open-label investigation; no blinding of assigned treatment will occur.

12.5. End of Study

The end of study is when 100 subjects complete the 1-year safety and cellulite severity evaluations. At the time of study termination, ongoing subjects receiving treatment will be followed through the Day 71 visit. The remaining enrolled subjects (in excess of the first 100 subjects to complete 1 year) will undergo early termination procedures in accord with the Schedule of Events (section [5](#)).

13. ASSESSMENT OF EFFICACY

13.1. Primary Efficacy Measurements

Although measures of efficacious drug effect (ie, durability of improvement) will be made during the observation phase before the study drug blind is broken in the double-blind study (EN3835-201), and thereafter to the end of study, emphasis is on the assessment of safety over 12 months after exposure to EN3835. Cellulite severity assessments will be made at scheduled intervals for both observation-only subjects (not receiving EN3835) as well as subjects who choose re-dosing or re-treatment with EN3835.

Digital Photography: Digital photography will be utilized to assess certain cellulite severity parameters at specific intervals (see Schedule of Events, [Table 2](#)) for subjects in the observation-only group as well as those electing to be re-treated or re-dosed with EN3835. At the Screening B visit for subjects electing to receive re-dosing or re-treatment, the Investigator or qualified designee will photograph each quadrant using a Sponsor-supplied standardized digital camera. The subject will be standing for each photography session and will be wearing a standardized photographic garment as described in the Photography Manual. The Investigator or qualified designee will photograph the selected quadrant as follows:

- Screening B (no dimple marking)
- Before and after dimple marking (prior to injections) on Days 1, 22, and 43 of each treatment course
- During the Day 71 visit (end of treatment phase/early termination) of each treatment course

All photographs from this study are the property of Endo and may be utilized for clinical development, scientific communication, marketing, regulatory purposes, and/or legal applications as required/desired by Endo.

13.1.1. Subject and Investigator Cellulite Assessments

As in the double-blind parent study, Investigator cellulite assessments are independent of the subject assessments. Therefore, all subject cellulite assessments must be completed before the Investigator's cellulite assessments are made. After both the subject's and investigator's assessments are completed, the subject's assessments will be revealed and compared to the clinician's assessments to determine eligible quadrants. If more than 1 quadrant is eligible, the subject will select one for treatment.

13.1.1.1. Patient-Reported Photonumeric Cellulite Severity Scale (PR-PCSS)

The PR-PCSS will be conducted for the purpose of assessing the severity of cellulite in the buttock or thigh; there are separate scales for buttocks or thighs. The scales are 5-level photonumeric scales developed specifically for patients and used by the subject to assess the severity of their cellulite in the quadrants by viewing digital images of each of their quadrants captured by photography at the visit; the ratings range from 0 (None) to 4 (Severe) with labels and descriptors to aid the subject in the assessments.

EN3835-202 Protocol Amendment 2

All subjects who enter the observation-only phase of the study will have the PR-PCSS evaluation at months 3, 6, 9, and 12.

For subjects electing re-treatment or re-dosing after the study drug blind is broken in study EN3835-201, a Screening B visit (Baseline) within 14 days before dosing Day 1 will occur. Subjects will have digital photographs taken of all 4 quadrants as done in the double-blind trial for qualifying purposes. Subjects will then perform the PR-PCSS for both buttocks ([Figure 1](#)) and thighs ([Figure 2](#)) and will be reminded of their proper use ([Appendix D](#)).

At the beginning of visits on Days 22, 43, and 71; digital photographs of the selected quadrant will be taken. If the buttock is the treated region, subjects will be given the PR-PCSS for the buttock to use to make their evaluation; if the thigh is the treated region, subjects will be given the PR-PCSS for the thigh to make their evaluation.

Figure 1: Patient-Reported Photonumeric Cellulite Severity Scale (PR-PCSS) for the Buttock

Patient Reported Photonumeric Cellulite Severity Scale (PR-PCSS) – Buttock

0 None

No evident cellulite

1 Almost None

A few superficial dimples or ridges

2 Mild

Several dimples or ridges of which most are superficial

3 Moderate

Many dimples or ridges of which most are somewhat deep

4 Severe

A lot of dimples or ridges of which many are deep covering most of the skin area

Produced by CANFIELD Scientific, Inc.

Version 8.0

© 2015 Endo Pharmaceuticals
Confidential – Not to be distributed

Figure 2: Patient-Reported Photonumeric Cellulite Severity Scale (PR-PCSS) for the Thigh

